If the subject is randomized to acetate: Control participants will need to arrange for a driver to and from the second session or we will provide a voucher for up to \$50 for them to take a taxi to Session 2 and up to \$50 for them to take a taxi home from Session 2. AUD participants will be accompanied to and from CeDAR for the second session. Two IVs will be placed by a CTCRC nurse or a physician on the study. One IV will be for infusion and one will allow blood draws without repeat sticks. The infusion IV and blood draw IV will be placed in separate arms to prevent infusate from confounding blood sample metabolite measures. The Session 2 timeline is illustrated in Figure 2. The first blood draw will be immediately after IVs are placed. Participant will then be escorted over to the Brain Imaging Center at the University of Colorado AMC for MRI scans. Participant will be blinded as to when they are receiving placebo and when they are receiving acetate. A placebo infusion will be started and continued through the first scan. The participant will be given the Subjective High Assessment Scale 7 (SHAS7), an analogue scale evaluating 7 subjective feelings of intoxication, before the first scan and after each scan (Schuckit et al., 2000). After each scan, participants will perform several motor tasks (psychomotor vigilance task, simple and choice reaction time task, and grooved pegboard task) to measure attention and arousal after placebo and drug. The participant will have the first MR scan of the brain. Immediately after the scan, the second blood sample will be obtained. One hour later, at 11:00 am, the placebo infusion will be switched to an acetate infusion and the participant will be placed in the MR scanner. The acetate will be prepared by the University of Colorado Hospital Research Pharmacy and will be based on methods of Jiang et al. (Jiang et al., 2013) (See below). The participant will have the second MR scan using the same protocol. Immediately following the second MRI scan, the third blood sample will be obtained. Then both IVs will be removed, participants will be given

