lunch and observed in the Brain Imaging Center for 1 hour. Participants will be given a stool sample kit and a prepaid return envelope for mailing the sample back to us. Participants will be reimbursed and allowed to go home with a driver or by taxi (details at top of paragraph). AUD participants will be accompanied back to CeDAR. All participants will receive a follow up call that evening. They will collect a stool sample the day after the scans and mail it back to us that same day.

If the subject is randomized to alcohol: The procedure is identical to that described for acetate with the following differences: (a) only one IV will be placed, for blood draws, (b) participant will receive a jello shot rather than an IV infusion. The participant is blinded as to when they will receive a placebo jello shot and when they receive an alcohol jello shot. The participant will be given a placebo jello shot 15 min before the first scan, and an alcohol jello shot 15 min before the second scan (Van Horn et al., 2006). Following the MRI, breath alcohol (BrAC) will be taken every 30 min until it reaches a level $\leq 0.02\%$, at which time participant will be allowed to go home with a driver or will be given a voucher for up to \$50 for a taxi (as described in first sentence of acetate section, above). We expect BrAC levels to be $\leq 0.02\%$ by 3 pm. All participants will receive a follow up call that evening.

[figure not shown]

Figure 2. Procedure for acetate and alcohol administration

Research Methods

IV acetate and placebo: Infusions will be prepared by the University of Colorado Hospital Research Pharmacy at the University Hospital the morning of the study. To maintain the single blind, the placebo bag will be labeled “Morning” and the acetate bag labeled “Afternoon.” A study team member will bring the infusion bags to the CTRC immediately before the study. Based on Jiang et al., acetate infusion will be 5 mg/kg/min for the first 7 minutes, followed by continuous infusion of 2.5 mg/kg/min for 68 minutes (Jiang et al., 2013). This rate results in safe plasma acetate levels of ~ 1.2 mM, comparable to acetate levels after moderate drinking (Jiang et al., 2013; Mason et al., 2006; Smith et al., 2007).

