2. Participants will need to arrange for a driver to and from the second session or we will provide a voucher for up to \$50 for them to take a taxi to Session 2 and up to \$50 for them to take a taxi home from Session 2.
3. CTSC nurse or a physician co-investigator will start IV, monitor infusions, and perform blood draws.
4. Participants will change into scrubs and provide a urine sample. Participants will be excluded from the MRI if positive for drugs, alcohol, or pregnancy.
5. Participant will enter MR scanner. There will be two scans, each ~1 hour. The first scan will be from 9-10am, the second scan will be from 11:30am-12:30pm.
6. Participants will either be in the acetate arm or in the alcohol arm of the study.
7. Participants receiving alcohol will have BrAC samples measured at 30 min intervals until BAC is $\leq 0.02\%$, at which time they will be allowed to go home with a driver or will be given a voucher for up to \$50 for a taxi (details in 2., above).
8. Participants receiving acetate will be observed for 1 hr to give acetate time to metabolize and then will be allowed to go home with a driver or will be given a voucher for up to \$50 for a taxi (details in 2., above).
9. The participant will change back into clothes and will be paid \$95 per scan. Thus they will be paid \$190 for completing all scans

Follow-up

1. Participant will receive a follow-up email or call from the PI on the evening of Session 2.

This study involves answering questionnaires, performing several motor tasks, having oral alcohol or an acetate infusion, and having a functional MRI of the brain. Breaches of confidentiality are a risk. It is necessary for participants to answer questions about private things like drug use, to rule out or diagnose substance dependence and other psychiatric conditions. Participants' names will be associated with a participant number to insure confidentiality. Behavioral data and imaging data will be stored using the participant number. All documents indicating the identity of participants will be kept in a locked room inside a locked file cabinet. Computer files include no identifiers except a code number, and will be password-protected. If the results of the study are published, data that might reveal the identity of any particular subject will be disguised. An MRI is a non-invasive routinely used procedure that poses minimal risk to participants.

Potential Risks

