Risks of alcohol. Ethyl alcohol in the amount used in the current study presents minimal risk to the participants. The amount of alcohol they receive will be less than the legal limit and is expected to produce mild intoxication. There is a chance of gastrointestinal irritation, nausea, vomiting, light-headedness, diarrhea with alcohol. These symptoms are self-limited and are expected to dissipate with time. Any subject who has never had alcohol in the past will be excluded. The PI will be with the participants for the length of the study until they leave.

Risks of acetate. Sodium acetate presents minimal risk to the participants. It can cause eye and skin irritation in the crystal form and ingesting large amounts may cause gastrointestinal irritation. The acetate will be in solution, and thus not expected to be an irritant. There is a rare possibility that a reaction may occur during or immediately after the infusion of acetate characterized by flushing or redness of the skin which may resemble a rash. No subject will receive both acetate and alcohol as they will be randomized to one arm. An established protocol will be used for the acetate infusions (Jiang et al., 2013; Mason et al., 2006). The infusion rate for this protocol results in plasma acetate levels of ~1.2mM, lower than another previous study (Akanji and Hockaday, 1990) that resulted in plasma acetate levels of 1.38 mM for healthy participants and 1.65 for diabetics. One study reported a mild metabolic alkalosis which was well tolerated by healthy participants (Smith et al., 2007). Participants will be observed until about 2:00 pm, 1.5 hours after infusion, for any adverse effects. The PI will be with the participants for the length of the study until they leave.

Venous Cannulation. Venous cannulation is a routine clinical procedure that carries minimal risks when performed by trained personnel. The major risk is pain and discomfort. It is possible bruising could occur in some participants. The risk of phlebitis or infection is very remote.

Blood draws. Blood will be drawn through the venous access catheter. Fifteen cc of blood per person will be taken, which is a minimal amount that does not pose significant risk to the participants.

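### The acetate-arm times are inconsistent; if the full second-scan slot is used, the only blood sample after acetate starts is drawn about 15 minutes after the infusion ends

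*Combined protocol and SAP*

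**What the plan says.** Section IV.C, Session 2 (acetate), sets the switch: "One hour later, at 11:00 am, the placebo infusion will be switched to an acetate infusion". The same sentence puts the participant in the scanner. The rate paragraph in IV.C (IV acetate and placebo) gives "5 mg/kg/min for the first 7 minutes, followed by continuous infusion of 2.5 mg/kg/min for 68 minutes" and expects a plasma level of about 1.2 mM.

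Section IV.D, Session 2, item 5, gives the slots: "The first scan will be from 9-10am, the second scan will be from 11:30am-12:30pm".

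Three blood samples are planned in IV.C:
- Sample 1: "The first blood draw will be immediately after IVs are placed".
- Sample 2, after the placebo scan: "Immediately after the scan, the second blood sample will be obtained".
- Sample 3: "Immediately following the second MRI scan, the third blood sample will be obtained". The next step is "Then both IVs will be removed".

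Under Risks of acetate, IV.D adds: "Participants will be observed until about 2:00 pm, 1.5 hours after infusion, for any adverse effects".

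IV.C refers to its procedure figure (Figure 2) for the session timeline and the timing of the draws. That figure is not in the text available for this review. Section IV.E, item 4, accepts that acetate kinetics are less well known than those of alcohol, and points to the infusion and the serum assay for control and knowledge of the level.

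**The concern.** Samples 1 and 2 come before any acetate, so sample 3 is the only measurement of what the infusion achieved. To describe exposure during imaging, it has to be drawn while acetate is running. The stated switch time, infusion length and scan slot together put it after the infusion has ended. Other parts of the text put it within the infusion or exactly at its end.

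The plan expects the level to fall once the infusion stops, since IV.D item 8 allows an hour of observation for acetate to be metabolized. A late sample would therefore read low, by an amount that depends on each person's clearance. If some scans fill the slot and others finish early, the gap would also vary between participants. The readable text does not ask for actual infusion or sampling times, so this could not be sorted out afterwards. At stake is whether the pilot can show that the intended acetate level was present during the scan.

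**Working it through.** **Inputs.** Switch 11:00 (IV.C). Infusion 7 min + 68 min (IV.C). Scan 1 from 9:00 to 10:00 and scan 2 from 11:30 to 12:30 (IV.D item 5). Total MR time 60 min, with listed sequences of 5 (T1), 6 (ASL) and 24 min (BOLD) (IV.C, MR acquisition). Observation until about 2:00 pm, stated as 1.5 h after infusion (IV.D). Plateau about 1.2 mM (IV.C). Alcohol raises plasma acetate 3-5 fold (section II).

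**The plan's own figures.**
- The one-hour interval: 10:00 + 1 h = 11:00. This agrees with the stated switch, so the interval and the clock time support each other.
- Infusion end implied by the risk text: 2:00 pm − 1.5 h = 12:30. From the switch: 11:00 + 75 min = 12:15, and 12:15 + 1.5 h = 1:45 pm. The 2:00 pm figure is not reproduced. It is approximate, so this mismatch is only supporting evidence.
- Start needed for a 12:30 end: 12:30 − 75 min = 11:15.

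**Where sample 3 falls under each reading.**

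| Reading | Infusion | Scan 2 | Sample 3 | Relative to infusion end |
|---|---|---|---|---|
| 11:00 switch, full IV.D slot | 11:00–12:15 | 11:30–12:30 | 12:30 | 15 min after |
| 11:00 switch, 60-min scan from 11:00 (IV.C alone) | 11:00–12:15 | 11:00–12:00 | 12:00 | 15 min before |
| 11:00 switch, only the listed 35 min from 11:30 | 11:00–12:15 | 11:30–12:05 | 12:05 | 10 min before |
| Infusion end at 12:30 (risk text) | 11:15–12:30 | 11:30–12:30 | 12:30 | 0 min |

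**Imaging, 11:00 switch and IV.D slot, sequences in the listed order.** The total is 5 + 6 + 24 = 35 min. ASL ends between 11:30 + 11 min = 11:41 and 12:30 − 24 min = 12:06, always before 12:15. BOLD ends between 12:05 and 12:30, so between 0 and 15 of its 24 minutes could fall after the infusion ends.

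**Size of the understatement if sample 3 is 15 min after the stop.** Assume the level is 1.2 mM at the stop and declines exponentially to a basal level of 1.2/5 = 0.24 or 1.2/3 = 0.40 mM. The documents give no half-life; 5 to 30 min is assumed.

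Level = basal + (1.2 − basal) × 2^(−15/half-life)

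| Half-life (min) | Fraction of the rise left | Level, basal 0.24 | Level, basal 0.40 |
|---|---|---|---|
| 5 | 0.125 | 0.36 mM | 0.50 mM |
| 10 | 0.354 | 0.58 mM | 0.68 mM |
| 15 | 0.500 | 0.72 mM | 0.80 mM |
| 30 | 0.707 | 0.92 mM | 0.97 mM |

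The extremes are 0.36/1.2 = 30% and 0.966/1.2 = 0.805, about 80%, of the intended level.

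**The case against.** The strongest reply is that the four main times can be laid on one timeline: infusion 11:00 to 12:15, scan 11:30 to 12:30, draw afterwards. That is correct. A reader might infer that the times are arithmetically impossible, and they are not. Two inconsistencies remain. IV.C places the participant in the scanner at 11:00 while IV.D starts the scan at 11:30, and the risk text needs an infusion end near 12:30 rather than 12:15.

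A reader might also infer that every third sample is at least 15 minutes late. The documents do not support that. The 15 minutes holds only if the IV.D slot is filled; the other readings put the draw up to 15 minutes before the infusion ends. The listed sequences need only 35 of the 60 minutes, so an early finish is plausible.

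The missing procedure figure may show the intended times. It could settle which reading is meant, but the text would still have to be aligned with it.

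The consequence is also limited. None of the statistical analyses in IV.F uses blood acetate as a covariate, filter or outcome, and IV.E says no dose-response will be obtained. A reader might infer that the comparison of AUD participants with controls is biased through differing clearance. The plan bases no such comparison on the blood level, and the documents give no clearance figures for either group. This part of the objection stands. What it leaves is the one measurement that could confirm exposure, in a pilot meant to inform a larger study.

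**Conclusion.** The point holds in a conditional form. The text gives inconsistent acetate-arm times, and following the stated switch and scan slot to the full puts sample 3 about 15 minutes after the infusion ends, with 0 to 15 minutes of BOLD possibly off infusion. In the listed order, ASL stays within the infusion. A sample at that time would read about 30% to 80% of 1.2 mM. That range rests on the assumed half-life and on the basal level derived from the 3-5 fold rise, so it illustrates the possible loss and does not estimate it.

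The paired CBF test, the sample size and alpha do not change. The matter is exposure verification in a feasibility study, and its weight is minor to moderate. The clock arithmetic is firm; which reading staff would follow is not known.

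**What to change.** State one clock in IV.C (Session 2), IV.D (Session 2, item 5) and IV.D (Risks of acetate), and check it against the procedure figure. Imaging and the third draw should both finish while acetate is running. Either of two options does this.

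- **Start acetate at 11:15, 75 minutes after scan 1.** The load ends at 11:22 and the infusion at 12:30, which fits the IV.D slot and the 2:00 pm figure. It also matches the alcohol arm, where the jello shot 15 minutes before scan 2 falls at 11:15. Both the one-hour interval and the clock time in IV.C must change. The cost is lead-in: scan 2 starts 15 rather than 30 minutes after the switch, and the earliest ASL start (11:35 in the listed order) is 20 rather than 35 minutes after it. Imaging should finish a few minutes before 12:30 to leave time for the draw.
- **Keep 11:00, and finish the listed sequences and the draw by 12:15.** This keeps the lead-in. Sequences run back to back from 11:30 end at 12:05, leaving 10 minutes for the draw. The IV.D slot and the risk text would need correcting.

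Under either option, add: *The third blood sample is drawn before the acetate pump is stopped.* Record the actual infusion start and stop, ASL start and third-sample times. If a scan overruns, record the gap and do not run the pump longer: 15 more minutes at 2.5 mg/kg/min would add 37.5 mg/kg to the planned 5 × 7 + 2.5 × 68 = 205 mg/kg. While editing, align the observation period, which is 1 hour in IV.C and IV.D item 8 but 1.5 hours in the risk text.

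The cost is a few edited times, one added sentence and four recorded times per session. Infusion rate, planned dose, sample size and alpha stay as they are.

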Practice effects: It is possible that differences in brain activity could reflect learning effects. To test for learning effects we administered two versions of the decision-making task to a healthy control, 2 hours apart. The two versions differed in the color and position of the decks and the scale of the magnitude of outcomes, while keeping the value of the decks balanced. The frequency of wins and losses was identical. There was no difference in Play response on good cards (93 vs. 95), bad cards (54 vs. 55), or on net score (good minus bad cards played) (39 vs. 40). *This lack of significant practice effect is consistent with a prior study showing stable performance on the Iowa Gambling Task, on which our task is based, given multiple times to controls (Xiao et al., 2013) and patients (Waters-Wood et al., 2012) and, together, suggest that there will not be a significant learning effect.*

IV. Research Methods

A. Outcome Measure(s):

Our goal in this pilot study is feasibility.

Preliminary outcome measures:

1. CBF before and after acute alcohol or acetate
2. Brain activity during decision-making before and after acute alcohol or acetate

B. Description of Population to be Enrolled:

This is a single blinded placebo controlled test of the effects of acetate and alcohol on brain function.

Inclusions-all: (1) age 21-55, (2) English proficient, (3) Participants must understand the nature of the study and must sign an informed consent; (4) be currently non-smoking.

Inclusions-moderate drinkers: (1) participants must be moderate drinkers (male: 1-14 drinks per week; female: 1-7 drinks per week); and (2) have drunk at least 2 drinks in one hour in the past; and have no history of dependence on drugs or alcohol.

Inclusions-AUD: (1) must meet DSM-V criteria for lifetime history of Alcohol Use Disorder (AUD)

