Potential participants will take part in a short interview at the Anschutz Medical Campus consisting of explanation of the study, screening for MRI compatibility, signing informed consent, and answering questions on drug and alcohol use.. Control participants will be randomized to the acetate or alcohol branch of the study but will not know which branch they are assigned to until Session 2. AUD participants will be assigned only to the acetate branch of the study. Participants will be asked to not drink alcohol for 48 hours prior to the study and to eat a light low-fat breakfast before coming to the University for Session 2. Session 2 (scan day) will be scheduled as soon as possible, about 1-2 weeks after Session 1.

Questionnaires:

- (1) Composite International Diagnostic Interview Substance Abuse Module (CIDI-SAM). Dependence on alcohol, cannabis and nicotine will be measured using the computerized CIDI-SAM, a structured interview designed for trained, lay interviewers (Cottler et al. 1995). (30 min)
- (2) Alcohol Use Disorders Identification Test (AUDIT). This test screens for alcohol abuse and average alcohol use (5 minutes)
- (3) Timeline Followback assessment. This assessment measures frequency and quantity of alcohol consumption for the most recent 1-3 months of alcohol use.

Session 2: Acetate or Alcohol and MRI scanning (~7 hours)

Research participants will arrive at the Clinical and Translational Research Clinic (CTRC) in the Leprino Building on the University of Colorado Anschutz Medical Campus (AMC) at 7:30 am, turn in their stool samples and 2 day food log, and provide urine samples to screen for alcohol, drugs and pregnancy.

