Decision-making task (Fig 2): Participants will play a modified version of the Iowa Gambling Task (Bechara et al., 1994) during fMRI scanning. The modified IGT assesses risk avoidance and sensitivity to negative outcomes (Tanabe et al., 2013; Thompson et al., 2012). We have many years of experience giving the task to substance users and controls. Briefly, participants are presented four decks of cards and instructed to earn as much hypothetical money as possible by choosing to either Play or Pass on a given deck. “Play” results in a single positive or negative monetary value, along with the running total. “Pass” results in no change. To perform well, participants must learn to Pass on the two bad decks that result in a net loss and Play on the two good decks that result in net gain over time. The payout of the decks is controlled on the frequency and magnitude of wins and losses. The decision period is 2 seconds, and the outcome period is 4 seconds, separated by a variable jitter of 0 to 4 seconds. There are 50 trials of each deck, 200 trials total, plus 40 baseline trials to control for motor effects, and 10 six-second fixation crosses presented in pseudorandom order. Total task scan time is 24 minutes consisting of two 12 minute runs. The task will be given twice, once in the morning and once in the afternoon. To reduce practice effects for the afternoon study, the color, win/loss amounts (but not the ratio of wins:losses), and the order of the decks will be changed.

[figure not shown]

Figure 3. Decision-making task and timing parameters.

D. Description, Risks and Justification of Procedures and Data Collection Tools:

Session 1

1. Consent Procedures: Participants will have time to ask questions and have the study explained by PI. They will fill out an MRI screening form to ensure safety prior to entrance to the scanner.
2. The session will be conducted in a private room to facilitate confidentiality. Data collected during the initial screening and between and after the MR sessions will be associated with the participant number only and will assess alcohol use (frequency, amount, and abuse/dependence symptoms).
3. Participants will be paid \$35 for completing Session 1.

Session 2

1. Participants will be asked to not drink alcohol for 48 hr prior to Session 2 and to eat a light low-fat breakfast on the day of Session 2 to avoid interference with alcohol absorption.

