BOLD fMRI pre-processing: After discarding the first 4 volumes for saturation effects, images will be corrected for movement with a 3-dimensional rigid body transformation. Participants with scan-to-scan head movement >2 mm will be excluded. Motion parameters will be modeled as nuisance variables. Images will be normalized to MNI space using the two step transformation procedure described for MR CBF. Images will be spatially smoothed with a 6 mm full-width-half-maximum isotropic Gaussian kernel, filtered to remove low-frequency fluctuations (128 s high pass filter), and corrected for temporal autocorrelation.

BOLD fMRI: Model specification and contrast of interest: The time series will be predicted by nine regressors, consisting of decision and outcome for each of the four decks, plus motor control. Motion parameters will be modeled as nuisance regressors. The stimulus function will be convolved with the canonical hemodynamic response function (HRF). We are primarily interested in effects of acetate or alcohol on brain activity during the decision phase of the task. The primary outcomes will be the contrast of Decision>motor control baseline and Outcome>motor control baseline. For each participant these contrast maps will be brought to the second level for subsequent ROI and whole-brain analyses.

Regions-of-interest (ROI): ROI and whole brain analyses will be conducted for outcome measures of CBF and fMRI BOLD activity. Six anatomically- defined ROIs will be based on the neural circuitry found to be involved during decision-making on the modified IGT and which overlap with brain regions showing altered signal after acute alcohol (Anderson et al., 2011; Bjork and Gilman, 2014). ROIs will be bilateral ventral striatum (VST), dorsal striatum, insula, and anterior cingulate cortex (ACC), orbitofrontal cortex (OFC), and dorsolateral prefrontal cortex (DLPFC). VST and DST will be manually drawn, based on published landmarks (Mawlawi et al., 2001). For the OFC, insula, ACC, and DLPFC, the automated anatomical labeling atlas (AAL) (Tzourio-Mazoyer et al., 2002) will be used. Figure 3 shows examples of VST=green, DST=orange, OFC=blue, insula=red.

[figure not shown]

Fig 3. Regions of interest

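### The task version is changed for the drug scan with no stated counterbalancing, so any version effect is aliased with drug in the within-arm BOLD and net-score contrasts

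*Combined protocol and SAP*

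**What the plan says.** All references are to the combined protocol and SAP.

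- **Task version.** Section IV.C, Decision-making task: "The task will be given twice, once in the morning and once in the afternoon". The sentence that announces the altered version begins "To reduce practice effects for the afternoon study, the color, win/loss amounts (but not the ratio of wins:losses), and the order of the decks will".
- **Condition at each scan, acetate branch.** Section IV.C, Session 2: "A placebo infusion will be started and continued through the first scan", and then "One hour later, at 11:00 am, the placebo infusion will be switched to an acetate infusion". The placebo bag is labelled for the morning and the acetate bag for the afternoon.
- **Condition at each scan, alcohol branch.** The participant is "given a placebo jello shot 15 min before the first scan, and an alcohol jello shot 15 min before the second scan".
- **What is randomised.** Section IV.C, Session 1: "Control participants will be randomized to the acetate or alcohol branch of the study". AUD participants all go to acetate. Neither placebo/drug order nor task version is allocated at random.
- **How the versions differ.** Section III, Practice effects, on the versions tried in one healthy control, has a sentence that begins "The two versions differed in the color and position of the decks and the scale of the magnitude of outcomes, while keeping the value of" and ends by saying that deck value was kept in balance. Win and loss frequencies were the same in both.
- **BOLD outcomes.** Section IV.F, Model specification: "The primary outcomes will be the contrast of Decision>motor control baseline and Outcome>motor control baseline". Ventral striatum is one of the six ROIs.
- **Analysis.** Section IV.F plans paired t-tests for the pilot ROI data in each branch, a whole-brain repeated-measures ANCOVA with drug as the within-person factor, and a repeated-measures ANOVA for net score adjusted for education. None has a version term.

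**The concern.** Each participant gives one placebo scan and one drug scan, and the within-person difference is the estimate. If everyone plays one version at the placebo scan and the altered version at the drug scan, that difference holds the whole version effect as well as the drug effect. A version term cannot rescue the analysis, because it would coincide with the drug term.

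The altered features include the monetary amounts, which are what the participant sees in the outcome period, and a contrast on that period is a primary BOLD outcome. The protocol discusses practice, order and diurnal effects but not version.

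What is at stake is the pilot's own product. The Power and Confidence Interval Width section says the study is to estimate the effect size and supply accurate parameters for the later study. A version offset would bias the BOLD part of that output, and would appear as a similar shift in both the acetate and alcohol branches.

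**Working it through.** **1. The plan's own figure on version equivalence.** Net score is good plays minus bad plays. First version: 93 − 54 = 39. Second version: 95 − 55 = 40. Both match Section III. They are behavioural counts from one person, so they give no variance estimate and no BOLD information.

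**2. Aliasing.** For participant *i*, write the drug-minus-placebo difference as

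D_i = τ + σ + v_i·ν + e_i,

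where τ is the drug effect, σ is everything tied to the second session (order, practice, time of day), ν is the effect of the altered version relative to the other, and v_i is +1 if the altered version is played at the drug scan and −1 if it is played at the placebo scan.

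As written, v_i = +1 for everyone, so the mean of D estimates τ + σ + ν. In a model with participant effects, a drug column and a version column, the last two columns are identical:

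| n | columns | rank as written | rank if versions are balanced |
|---|---|---|---|
| 7 (AUD, scanned target) | 9 | 8 | 9 |
| 15 (controls per aim, usable target) | 17 | 16 | 17 |
| 20 (controls per aim, scanned target) | 22 | 21 | 22 |

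This result needs no assumption about the size of ν.

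**3. Size, by assumption.** The documents give no value for ν. Let δ be ν divided by the SD of the paired difference, and set τ = σ = 0. The paired t statistic is then noncentral t with n − 1 df and noncentrality δ√n. The probability that a two-sided 5% test is significant is:

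| δ (assumed) | n=15: noncentrality | n=15: P(significant) | n=7: P(significant) |
|---|---|---|---|
| 0.1 | 0.387 | 6.5% | 5.6% |
| 0.2 | 0.775 | 11.2% | 7.4% |
| 0.3 | 1.162 | 19.2% | 10.3% |
| 0.5 | 1.936 | 43.8% | 20.1% |

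**4. Can the planned checks rule out ν?** Section IV.C, Order effects, plans to scan two healthy controls twice in one day with no intervention. It does not say which task version is used at each scan. With n=2 there is 1 df and the critical t is 12.7; power is 5.2% at δ = 0.2 and 7.9% at δ = 0.8. Neither this check nor the single behavioural pilot is informative about ν.

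**5. Balanced versions.** With a participants on one version order and b on the other (a + b = n):

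- Raw mean of D: τ + σ + ν(a − b)/n. An 8/7 split leaves ν/15 and a 4/3 split leaves ν/7.
- Equally weighted average of the two order-specific means: τ + σ, with ν removed exactly.
- Variance relative to the unadjusted mean: n²/(4ab). For 8/7 this is 225/224 = 1.004; for 4/3 it is 49/48 = 1.021.
- Residual df fall from 14 to 13 and from 6 to 5, so the 97.5% t quantile goes from 2.145 to 2.160 and from 2.447 to 2.571. For the same residual SD, the confidence interval widens by (2.160/2.145)·√1.004 = 1.01 at n=15 and (2.571/2.447)·√1.021 = 1.06 at n=7.

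σ stays in the estimate in every case.

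**The case against.** **The text does not say that versions are fixed.** A reader might infer that the protocol prescribes the same version for everyone each morning. It does not: it says the task changes for the second scan, and a change within each person is compatible with counterbalancing. What can be said is that no counterbalancing is stated and that the plain reading is a fixed order. This stands as a limit on the point.

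**The versions were built to be equivalent.** Deck value is balanced, win/loss frequency is identical, the win:loss ratio is kept, the money is hypothetical, and each contrast is taken against a motor control baseline. The stated main interest is the decision phase, whereas amounts are shown at outcome. Net score counts plays, so payoff scale does not enter it arithmetically. All this makes a small effect plausible. It does not show that BOLD is equivalent, and the outcome contrast is also listed as primary.

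**It is a feasibility pilot, already confounded with session.** Both are true. Rejection rates are therefore not the main harm. Section IV.E justifies same-day scanning by the burden of a second day, but nothing comparable ties version to session, so this component can be avoided.

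**Much of the trial is untouched.** This also stands. CBF comes from a separate ASL acquisition, not from the task. A version offset shared by all participants cancels in the AUD-versus-control comparison of change (hypothesis 1c) and in acetate versus alcohol, unless version interacts with group.

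**Conclusion.** The point holds as a cheap design improvement. On the plain reading of the protocol, task version is fully aliased with drug in the within-arm placebo-versus-drug contrasts of BOLD and net score, and no analysis of the data as collected could separate them. This rests on the absence of any stated counterbalancing, and on taking the versions described in Section III to be those used in the trial; a sentence confirming the allocation would settle it.

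The size of the version effect is unknown. The range of 6.5% to 44% at n=15 depends wholly on assumed effects of 0.1 to 0.5 SD and is only illustrative. The practical consequence is a possible bias, of unknown sign and size, in the BOLD effect estimate taken forward to the larger study.

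Two stronger readings are not supported. The documents do not show that a version effect exists, or that rescaled hypothetical payoffs alter activity in the planned ROIs. Nor would balancing versions yield a clean drug effect, because everything else tied to the second session would remain in the estimate.

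**What to change.** In the Decision-making task section, state how versions are allocated. Within each of the three groups (control-acetate, control-alcohol, AUD-acetate), assign version order A-then-B or B-then-A in balanced blocks and record it. Leave placebo/drug order as it is.

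In Section IV.F, estimate the within-arm BOLD and net-score drug contrasts as the equally weighted average of the two version orders, or equivalently include a version term. A raw mean is not enough when the groups split unevenly. If versions are already counterbalanced, say so and add the term.

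In the Order effects paragraph, say which versions the two no-drug participants play. In Section IV.E, where diurnal variation is already acknowledged, add that session order and practice are also confounded with drug.

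The cost is one allocation list, a few protocol sentences, one residual df, and variance inflation of about 0.4% at n=15 and 2% at n=7. Section III indicates that two versions already exist.
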